### 3 OBJECTIVES AND ENDPOINTS

OBJECTIVES	ENDPOINTS	JUSTIFICATION FOR ENDPOINTS
Primary		
To determine whether booster dosing with the Moderna COVID-19 vaccine can induce humoral immune responses in patients with hematologic malignancies who did not have an adequate response to prior first vaccination with any of the SARS-CoV2 vaccines authorized for use in the USA.	The primary endpoint is the observed rate of anti-SARS-CoV2 IgG antibody seroconversion (from negative to positive) measured 28 days (+/- 3 days) following a booster dose of the Moderna COVID-19 vaccine.	The described assay measures antibodies against the SARS-CoV2 spike protein, which is what the Moderna vaccine is designed to induce. This is a commercially available assay which is already in use at the Karmanos Cancer Center and Detroit Medical Center.
Secondary		
1. To determine whether booster dosing with the Moderna COVID-19 vaccine is safe in patients with multiple myeloma, AL amyloidosis, or other hematologic malignancies.  2. To compare the humoral immune responses between the patients who had a WEAK POSITIVE RESPONSE to prior vaccine (Cohort 3) vs. those with NO RESPONSE to prior vaccination (Cohorts 1 and 2).  3. To descriptively summarize clinical and immune characteristics which contribute to likelihood of	1. AEs and SAEs observed in participants, determined according to daily phone calls or video chats for 1 week following vaccine administration, and then weekly after that until 4 weeks after vaccination (Pts will also be examined 4 weeks after vaccination).  2. Humoral immune responses measured 28 days (+/- 3 days) following a booster dose of the Moderna COVID-19 vaccine.  3.a. Clinical characteristics of enrolled participants, including treatment history, disease, status, or presence	This is an early experience with booster dosing using the Moderna COVID-19 vaccine. Though new AEs/SAEs are not expected, it is important to document the safety of this intervention.  Clinical factors related to disease or immune status may be associated with likelihood of responding to booster

OBJECTIVES	ENDPOINTS	JUSTIFICATION FOR ENDPOINTS
responding to booster dosing with the Moderna COVID-19 vaccine.	of immunoparesis (i.e., hypogammaglobulinemia)  3.b. Characterization of other aspects of patients' immune status through T-cell profiling, including analysis of T-cell receptor (TCR) reactivity against COVID-19 antigens	dosing (or failing to respond), so detailed documentation of these factors is important.

## 4 STUDY DESIGN

### 4.1 OVERALL DESIGN

The specific hypothesis being tested is that it may be possible to induce a protective humoral immune response with a booster dose of the Moderna COVID-19 vaccine in patients with hematologic malignancies who did not have an adequate response to first vaccination with any of the available COVID-19 vaccines. To test this hypothesis, the Karmanos Cancer Institute will conduct a Phase II single-stage trial in which patients with a negative or weak positive anti-SARS-CoV2 IgG antibody test (defined as <1.00 S/CO and 1.00-1.99 S/CO, respectively) will receive a single standard dose of the Moderna COVID-19 vaccine intramuscularly, and then have anti-SARS-CoV2 IgG antibody levels checked 28 days (+/-3 days) later. This will be a single institution trial which will be open to enrollment at the Detroit (Dresner) and Farmington Hills (Weisberg) treatment facilities. As this is an open label Phase 2 trial, there is no randomization or stratification involved. There will be three cohorts enrolled: a cohort of MM and AL amyloidosis patients with an anti-SARS-CoV2-IgG Ab level of <1.0 S/CO, a cohort of patients with other hematologic malignancies (HM) with an anti-SARS-CoV2-IgG Ab level of <1.0 S/CO and a mixed MM/AL/HM cohort in which patients have an anti-SARS-CoV2-IgG Ab level of 1.0-1.99 S/CO ("low-positive cohort"). Each cohort will be of sufficient size to evaluate the efficacy of the intervention separately, and all secondary endpoints will be analyzed on the entire combined patient set.

### 4.2 SCIENTIFIC RATIONALE FOR STUDY DESIGN

A Phase II trial design using the surrogate endpoint of humoral seroconversion to assess vaccine response is more appropriate than using SARS-CoV2 infection rate because of the unpredictable timing and frequency of the latter. Immune response should be evident in the first few weeks after vaccination in any individual who is ultimately destined to respond. The size of the trial was selected so as to be sufficient to determine whether the vaccine booster can induce humoral immune response.

### 4.3 JUSTIFICATION FOR DOSE

The dose of the Moderna COVID-19 vaccine used is the standard dose: 0.5 mL, administered intramuscularly.

#### 4.4 END OF STUDY DEFINITION

The trial will be concluded after the last patient is enrolled and has completed the 28-day post-vaccination follow-up visit.

### 5 STUDY POPULATION

#### 5.1 INCLUSION CRITERIA

In order to be eligible to participate in this study, an individual must meet all of the following criteria:

1. Provision of signed and dated informed consent form
2. Stated willingness to comply with all study procedures and availability for the duration of the study
3. Male or female, aged 18 years of age or older
4. Previously diagnosed with MM/AL amyloidosis (Cohorts 1 or 3) or other hematologic malignancy (Cohorts 2 or 3).
5. Previously received any one of the available COVID-19 vaccines (between 4 and 36 weeks prior to enrollment)
6. Anti-SARS-CoV2 IgG antibody titer of results less than 1.0 units (Cohorts 1 and 2), or 1.0-1.99 units (Cohort 3). Antibody titers will be measured within 14 days of enrollment.
7. If currently receiving potentially immunosuppressive anti-neoplastic therapy for their underlying hematologic condition, a two-week interruption in therapy before and after the booster dose of vaccine is ENCOURAGED BUT NOT REQUIRED (physician discretion).

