## 1.2 SCHEMA

### ***Flow diagram***

### 1.3 SCHEDULE OF ACTIVITIES (STUDY CALENDAR)

Procedures	Screening/Consenting Day -14 to -1	Enrollment/Baseline Visit 1, Day 1	Days 2-8, 15, 22 (+/- 1 day) Phone/Text/Email	Study Visit 2 Day 28 +/- 3 days
Informed consent	X			
Demographics	X			
Medical history update	X			X
Administer vaccine dose		X		
Concomitant medication review	X			X
Physical exam	X			X
Vital signs	X	X		X
Height	X			
Weight	X			X
Performance status f	X			X
Hematology a	X			X
Serum chemistry b	X			X
Cardiac Biomarkers e	X		(X) d	X
Coagulation testing c	X			
Anti-SARS-CoV2 IgG Ab titer	X			X
Patient-reported AE assessment		X	X---X	X
Correlative blood sample collection	X			X

a. CBC with diff  
b. standard CMP, uric acid, magnesium, phosphorus, LDH, quantitative immunoglobulins (IgG, IgA, IgM)  
c. PT/INR, PTT, fibrinogen  
d. only if patient reports chest pain, palpitations, shortness of breath, or other symptoms suggesting cardiac etiology  
e. hsTrop I and BNP  
f. See Appendix 1: ECOG Performance Status

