#### 5.2 EXCLUSION CRITERIA

An individual who meets any of the following criteria will be excluded from participation in this study:

1. Daily corticosteroids at a dose equivalent to Prednisone 20 mg/day or greater during the period two weeks before enrollment to the trial. *Intermittent* steroid dosing at or above this level is permitted (i.e., weekly dexamethasone dosing as part of myeloma therapy)
2. History of previous severe reaction to any available COVID-19 vaccine (defined as any Grade 3 or higher reaction)
3. Febrile illness within 3 days of booster dosing.
4. Documented SARS-CoV2 infection within 2 weeks of enrollment.
5. Less than 3 months post-autologous or allogeneic stem cell transplant (NOTE: transplant between initial standard vaccine administration and enrollment is NOT otherwise grounds for exclusion from participation).

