### 5.3 LIFESTYLE CONSIDERATIONS

Patients who are diagnosed with an acute SARS-CoV2 infection in the post-vaccine follow-up period (i.e., between the vaccine and the serologic testing for response to vaccine) will be considered non-evaluable for the primary endpoint of the trial.

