## 8 STUDY ASSESSMENTS AND PROCEDURES

### 8.1 EFFICACY ASSESSMENTS

**Please refer to the Study Calendar (Section 1.3) for a complete list of protocol-related assessments.**

A blood specimen collection will be performed on day 28 (+/- 3 days) after the administration of the booster dose of the Moderna mRNA COVID-19 vaccine. An anti-SARS-CoV2 IgG Ab titer will be measured using this sample. This is the primary efficacy assessment being performed as part of this trial.

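### The vaccination and infection windows run from enrollment, but the qualifying titre may be drawn up to 14 days earlier, so some baselines can precede a complete response

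*Combined protocol and SAP*

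**What the plan says.** Inclusion criterion 5 (Section 5.1) requires "Previously received any one of the available COVID-19 vaccines (between 4 and 36 weeks prior to enrollment"; it does not say which dose of a series starts the count. Criterion 6 sets the cohort by titre, "titer of results less than 1.0 units (Cohorts 1 and 2), or 1.0-1.99 units (Cohort 3", and adds: "Antibody titers will be measured within 14 days of enrollment". Exclusion 4 (Section 5.2) removes "Documented SARS-CoV2 infection within 2 weeks of enrollment".

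The study calendar (Section 1.3) puts enrollment on Day 1, the day of the booster. It marks the titre in the column "Screening/Consenting Day -14 to -1" and again at Day 28, but not on Day 1.

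On time to response, Section 4.2 says: "Immune response should be evident in the first few weeks after vaccination in any individual who is ultimately destined to respond". Section 8.1 gives the booster about four weeks: "A blood specimen collection will be performed on day 28 (+/- 3 days) after the administration of the booster dose". Section 5.3 deals with later infection: "Patients who are diagnosed with an acute SARS-CoV2 infection in the post-vaccine follow-up period" are non-evaluable for the primary endpoint.

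Section 9.3 tests each cohort of 52 against a 5% rate of spontaneous rise and needs at least 6 responders at the 2.0 S/CO threshold.

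**The concern.** Both windows are meant to separate the earlier vaccination or infection from the booster. They do so relative to enrollment, yet the measurement that labels a patient as having no or a weak response is the screening titre. No section sets a minimum interval between prior vaccination or infection and that titre.

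A patient sampled early may still be building antibody. If that titre later passes 2.0 S/CO, the patient counts as a booster responder. With no control arm, nothing in the analysis separates such a rise from a booster effect. Cohort 3 is exposed in the same way, since a titre of 1.0-1.99 may still be climbing. At stake are the cohort label and the attribution of a few responses, in a test where 6 responses are enough.

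**Working it through.** **Intervals.** Day -14 is taken as 14 days before enrollment, in line with criterion 6.

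- Shortest interval from vaccination to titre: 28 - 14 = 14 days. The booster is given 28 +/- 3 days.
- An infection documented 15 or 16 days before enrollment is not excluded. The titre may follow after 15 - 14 = 1 or 16 - 14 = 2 days.

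**The plan's own rule.** With X ~ Binomial(52, p), P(X >= 6) is 0.0445 at p = 0.05 and 0.812 at p = 0.15. The smallest sample size that meets both limits is 52. The stated design reproduces. The error passes 5% once the true null rate exceeds about 5.15%, which is (0.0515 - 0.05) x 52 = 0.08 extra expected responders.

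**Share sampled early (assumption).** The documents give no distribution. Take vaccination dates uniform over 4 to 36 weeks (28 to 252 days, a span of 224 days) and titre dates uniform over 1 to 14 days before enrollment (mean 7.5 days). A patient whose titre is drawn d days before enrollment is sampled before 28 days with probability d/224. On average f = 7.5/224 = 3.3%, or 52 x 7.5/224 = 1.7 patients per cohort.

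**Effect on false success.** Let q be the chance that an early-sampled patient passes the threshold without any booster effect; the documents do not give it. Added to a full 5% null rate, p = 0.05 + 0.95 x f x q.

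| q | p | P(X >= 6 of 52) |
|---|---|---|
| 0 | 0.0500 | 4.5% |
| 10% | 0.0532 | 5.7% |
| 25% | 0.0580 | 7.9% |
| 50% | 0.0659 | 12.6% |

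The last value is 12.4% if f is first rounded to 3.3%.

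**Extreme sampling pattern.** If every titre were drawn at Day -14, f = 14/224 = 6.25% (3.3 of 52), and the same q values give 6.9%, 11.9% and 23.2%.

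**If the 5% null already includes these rises.** Under uniform dates they add at most f x 1 = 3.3 points, even if every early-sampled patient crosses. That fits within 5%, so the error stays at or below 4.5% as long as other spontaneous rises fit in the remainder.

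The infection route is not in these figures, because the documents give no frequency for it.

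**The case against.** The strongest reply is that the null hypothesis in Section 9.3 is itself an allowance for titres that rise without the booster. Late responses to earlier vaccination belong there, and adding them to a full 5% may count them twice. This stands as a limit on the size. It does not close the gap, because the 5% has no stated source and the rule has almost no slack above it.

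A reader might infer a badly inflated error. If 70% of early-sampled patients crossed anyway, p = 0.05(1 - f) + 0.70f would give false-success chances of about 26% and 56% at f = 5% and 10%. The documents support neither input. The 70% has no source, and these patients were selected for a haematologic malignancy and a low titre. Both shares also exceed the 3.3% obtained from uniform dates.

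A reader might also infer that infection between the titre and Day 1 goes unhandled. It does not: that period lies inside exclusion 4. What remains is infection documented just before the titre. Section 7.2 lets the investigator withdraw a participant for documented infection, but that is discretionary. Section 8.2 shows that including previously infected patients is deliberate, so prior infection as such is not the fault.

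Finally, day 14 is not shown to be too early. The efficacy table in Section 2.3.2 counts cases from 14 days after dose 2, though in a general trial population. Section 4.2's few weeks does not settle it. The inconsistency is that the booster is allowed 28 +/- 3 days while the earlier vaccine can be judged on half of that.

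**Conclusion.** The gap is in the text, and no other section closes it. Any cohort can admit patients whose response to an earlier vaccination or infection is not yet complete at the qualifying titre, and a later rise is credited to the booster. Under uniform dates, and with late rises added to a full 5% null rate, false success moves from 4.5% to roughly 6% to 13% per cohort for q between 10% and 50%. It does not move at all if the 5% already covers these rises. The share, q and the independence of the two date distributions are all assumptions.

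A reader might infer that the sample size, decision rule or stated power is wrong. They are correct; the issue is attribution in an uncontrolled design. Nor do the documents support a serious loss in the secondary comparison. Lifting Cohorts 1 and 2 from 15% to 18% would need f x q = 0.03/0.85 = 3.5%, more than the whole early-sampled share under uniform dates, and Cohort 3 has the same exposure. This should be fixed, but it does not invalidate the design.

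**What to change.** Count both windows back from the date of the qualifying titre sample. For vaccination, keep the protocol's 4-week figure and state that it runs from the last prior dose. For infection, the sponsor should set the interval before the titre; the period from titre to Day 1 is already covered by exclusion 4. Record the dates of the last prior dose, any documented infection and the titre on the case report form.

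Pre-specify a sensitivity analysis of the response rate in each cohort that leaves out patients whose titre was drawn less than 4 weeks after prior vaccination or within the chosen interval after a documented infection. Report it with its own denominator and 90% confidence interval, since the rule of 6 in 52 does not carry over to a smaller set.

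The nucleocapsid antibody in the Bio-Plex panel (Section 8.2) should not be the safeguard. The calendar places the pre-dose correlative sample at screening, alongside the titre, so an infection 1 to 2 days old would probably be missed there too.

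The cost is a change of wording in two criteria and one added analysis. A few patients need a later or repeat titre, including some found through routine clinic testing (Section 5.5), and enroll up to about two weeks later. Sample size and decision rule are unchanged. The change is best made before enrollment, because a baseline cannot be redrawn after dosing.

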**Study Population:**

Three 52-person cohorts. Cohort 1: multiple myeloma and amyloidosis patients who did not develop an anti-spike antibody titer of >1 S/CO after prior COVID-19 vaccination. Cohort 2: patients with other hematologic malignancies who did not develop an anti-spike antibody titer of >1 S/CO after prior COVID-19 vaccination. Cohort 3: patients with multiple myeloma, amyloidosis, or other hematologic malignancy who had a "weak positive" response to prior COVID-19 vaccine, defined as an anti-spike antibody titer of 1-2 S/CO. Patients with a history of severe prior adverse vaccine reaction are excluded. Patients must be 18 yo or older.

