### 5.5 STRATEGIES FOR RECRUITMENT AND RETENTION

Potential participants will be identified from amongst the hematologic malignancy patients seen at the Karmanos Cancer Institute. Post-vaccination anti-SARS-CoV2 IgG Ab testing is being conducted as part of routine clinic practice at the cancer center, so many patients meeting eligibility criteria are already identified. We anticipate the majority of participants will be enrolled within a month of the trial opening. We also anticipate that patients may be referred for participation from within the McLaren Network or from other hospital networks, or they may self-refer. We also plan to inform myeloma, amyloidosis, and hematologic malignancy patient support groups across the state of Michigan using IRB-approved communications. African American patients who have previously received any of the available COVID-19 vaccines are having anti-SARS-CoV2 IgG Ab titers checked at the same frequency as other patient populations, and thus will have equal opportunity to participate in this trial. There is no compensation provided for participating in this trial.

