## 9.3 SAMPLE SIZE DETERMINATION

The specific hypothesis being tested is that it may be possible to induce a protective humoral immune response with a booster dose of the Moderna COVID-19 vaccine in patients with hematologic malignancies who did not have an adequate response to first vaccination with any of the available COVID-19 vaccines. The null hypothesis is that 5% or less of patients who have an anti-SARS-CoV2-IgG Ab titer of less than 2.0 S/CO will spontaneously develop a higher titer. We hypothesize that at least 15% of patients in each cohort will develop a titer of 2.0 S/CO or greater in response to the vaccine, without toxicity in excess of that previously described amongst COVID-19 vaccine recipients.

Thus, the sample size for each cohort of this trial was determined using the Phase 2 single-arm single-stage design based on the following statistical assumptions:  $p_0=5\%$ ,  $p_1=15\%$ , 1-sided alpha = 5%, and power = 80%. In this case, 52 patients would be enrolled to each of the three cohorts. In each cohort, at least 6 patients would need to develop an anti-SARS-CoV2-IgG Ab titer of  $>2.0$  S/CO to reject the null hypothesis. Therefore, a total of 156 response-evaluable patients would be enrolled in this 3-parallel cohort, single-arm, single-stage Phase 2 trial. Given that the study intervention is a single vaccination, and the primary endpoint requires a single visit for a physical a blood sample collection, there should be relatively few non-evaluable patients. Patients who are non-evaluable for the primary endpoint will be replaced only if it becomes evident that this is needed to determine whether or not the primary endpoint is met in any/all of the cohort(s). We expect this will amount to no more than 5 additional patients in any of the three cohorts, so the maximum number of enrolled participants is 171 (= 57 x 3 cohorts).

The size of the trial will also permit a comparison of the likelihood of developing a strong positive response amongst the pooled participants form Cohorts 1 and 2 (i.e., the participants with NO RESPONSE to prior vaccination) versus the participants in Cohort 3 (i.e., the patients who had a WEAK POSITIVE RESPONSE to prior vaccine) as the second secondary objective. We hypothesize that the absolute difference in response rate between Cohort 3 vs. Cohort 1+2 is 20% or more against the response rate of 15% in Cohort 1+2 (i.e., Cohort 3: 35% vs. Cohort 1+2: 15%). The sample sizes of 156

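### Cohorts 1 and 2 are labelled as non-responders to first vaccination but are selected on current titre alone, so a positive cohort does not by itself show response in patients who never responded

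*Combined protocol and SAP*

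**What the plan says.** **The label.** The synopsis (Study Population) defines Cohort 1 as "multiple myeloma and amyloidosis patients who did not develop an anti-spike antibody titer of >1 S/CO after prior COVID-19 vaccination" and Cohort 2 as "patients with other hematologic malignancies who did not develop an anti-spike antibody titer of >1 S/CO after prior COVID-19 vaccination". Section 9.3 calls the two cohorts pooled "the participants with NO RESPONSE to prior vaccination". The primary objective (sections 1.1, 3 and 9.1.1) likewise concerns patients whose response to first vaccination was inadequate.

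**The rule.** Section 5.1 admits patients vaccinated "between 4 and 36 weeks prior to enrollment". It assigns Cohorts 1 and 2 by a titre below 1.0 and Cohort 3 by a titre of 1.0-1.99, and on timing says only "Antibody titers will be measured within 14 days of enrollment". Section 4.1 also assigns cohorts by titre level alone. No criterion asks for an earlier negative titre or excludes an earlier positive one. Section 5.2 requires at least 3 months since any stem cell transplant, then adds that "transplant between initial standard vaccine administration and enrollment is NOT otherwise grounds for exclusion from participation".

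**The analysis.** Section 9.4.1 gives the response rate with a 2-sided 90% interval by cohort and for Cohorts 1+2, Fisher's exact test for Cohort 3 versus Cohorts 1+2, and exploratory univariable logistic models on patient characteristics. It has no breakdown by earlier titre or by time since vaccination.

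**The concern.** A patient who seroconverted after first vaccination and has since dropped below 1.0 meets every criterion for Cohort 1 or 2 and is analysed as having had no response. Restoring a lost response and inducing one that never occurred are different questions, and the stated objective is about the second. The threshold is low, 6 of 52, so a modest minority of such patients could matter.

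The same applies to Cohort 3: a current 1.0-1.99 may be what is left of a stronger response. The planned comparison of Cohort 3 with Cohorts 1+2 is framed as weak versus absent prior response, but both sides may be mixtures. At stake is what the trial may conclude about non-responders, in the primary objective and in a secondary comparison for which section 9.3 claims 82.7% power.

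**Working it through.** **Inputs from section 9.3:** p0 = 5%, p1 = 15%, 1-sided alpha 5%, power 80%, n = 52 per cohort, reject at 6 or more responders.

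**The plan's own figures.** With X ~ Binomial(52, p):
- P(X ≥ 6 | p = 0.05) = 0.0445 and P(X ≥ 6 | p = 0.15) = 0.812. A search for the smallest n meeting both targets also returns 52 with threshold 6, so the design reproduces.
- Exact enumeration of the 1-sided Fisher test (52 versus 104, 35% versus 15%) gives power 0.833 against the stated 0.827, which is close enough.

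**Inputs not in the documents (assumed):** the share f of a cohort that are waned responders, and their response rate r to the booster. Never-responders are set at the null rate of 5%.

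**Formula.** The cohort's true rate is q = f·r + (1 − f)·0.05, and the rejection probability is P(X ≥ 6 | n = 52, q). For example, f = 0.10 and r = 0.40 give q = 0.040 + 0.045 = 0.085.

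| Waned share f | Their response r | q | P(≥ 6 of 52) |
|---|---|---|---|
| 0 | – | 5.0% | 4.5% |
| 2% | 30% | 5.5% | 6.5% |
| 5% | 30% | 6.25% | 10% |
| 5% | 40% | 6.75% | 14% |
| 10% | 20% | 6.5% | 12% |
| 10% | 40% | 8.5% | 28% |
| 10% | 60% | 10.5% | 47% |
| 10% | 70% | 11.5% | 56% |
| 20% | 40% | 12.0% | 60% |
| 20% | 60% | 16.0% | 86% |
| 20% | 70% | 18.0% | 93% |

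**Check with a fixed count.** Let k patients be waned, so that the total is Binomial(k, r) + Binomial(52 − k, 0.05). With k = 5 (5/52 = 9.6%) and r = 40%, 60%, 70%, P(≥ 6) is 25%, 45%, 56%. With k = 10 (19.2%) it is 60%, 90%, 97%. The picture is the same.

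**What the table measures.** In every row with waned patients q exceeds 5%, so the literal null (5% or less) is false for that cohort and rejecting it is correct. The table shows how often a cohort would be declared positive while its never-responders sit at 5%.

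**Restricting the test to confirmed non-responders within the 52.** With threshold 6, power at 15% is P(X ≥ 6 | n = 47) = 0.727 and P(X ≥ 6 | n = 42) = 0.617, against 0.812 at 52.

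**The case against.** The strongest reply is that the tested population is defined by current titre throughout the operative text. The null in section 9.3 concerns patients who have a titre below 2.0, and sections 4.1 and 5.1 match it. A patient whose titre has fallen belongs to that population, and the objective does not say when adequacy of the earlier response is judged. This stands as far as the test goes. A reader might infer from the table that type I error is inflated, or that the 52/6 rule is invalid. Neither follows, because the table gives power against a mixture. The reply does not rescue the label or a conclusion drawn from it.

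Second, the documents give neither the waned share nor its response rate, and low inputs give only 6.5% to 14%. That stands. A reader might infer that waned responders will carry a cohort; the documents show only that they could.

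Third, section 5.5 says "Post-vaccination anti-SARS-CoV2 IgG Ab testing is being conducted as part of routine clinic practice at the cancer center" and that many eligible patients are already identified. Patients found through an earlier low routine titre would tend to reduce the waned share. This is fair, but it describes recruitment and is not a criterion. The section does not say that titres are serial or taken soon after vaccination, and it also expects outside referrals and self-referrals. For the same reason, one cannot assume that an early titre exists for every patient.

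Fourth, section 8.2 already collects treatment history, which should capture transplant, and leaves other variables to be decided. Earlier titre and weeks since vaccination are not named in section 8.2 or 9.4.1, so the gap is narrow but open.

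**Conclusion.** The mismatch between label and rule is real, and nothing elsewhere in the plan closes it. It limits interpretation; the test itself is not in error. A cohort reaching 6 of 52 would support a statement about patients with a current titre below 1.0. It would not, without more, support one about patients who never responded to first vaccination, and Cohort 3 versus Cohorts 1+2 compares current titre bands, not prior response.

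The size is uncertain. With never-responders at 5%, the chance of a positive cohort runs from 6.5% (2% waned, 30% responding) through 12-56% (10% waned, 20-70% responding) to 60-93% (20% waned, 40-70% responding), against 4.5% with none. These figures rest wholly on assumed shares and response rates. The point deserves action because it bears on the primary conclusion and the remedy is cheap.

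**What to change.** - **Wording.** In the synopsis, 9.3 and 9.4.1, describe the cohorts and the conclusion by current titre: below 1.0 for Cohorts 1 and 2, 1.0-1.99 for Cohort 3.
- **CRF.** Record any earlier post-vaccination titre on file with its date, weeks from last vaccine dose to the screening titre, and any transplant in between.
- **Section 9.4.1.** Keep the 52/6 test unchanged. Add, for all three cohorts, a descriptive response rate with 90% interval by earlier titre: documented and below the cut, with weeks from vaccination to that titre shown; documented at or above the cut; none on file. The cut is 1.0 for Cohorts 1 and 2 and 2.0 for Cohort 3. Give the same summary by weeks since vaccination.
- **Claims.** Limit statements about patients who did not respond to first vaccination to those with a documented early negative titre, and define early before the data are analysed. Without that timing, a titre drawn after waning would pass as non-response.

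**Cost.** Chart abstraction and text changes; no added patients, blood draws or eligibility rules. The confirmed subset will be smaller than 52, will depend on what is in the chart, and should stay descriptive, since power at 15% with threshold 6 would be about 73% with 47 patients and 62% with 42.
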